The purpose for Amendment 2 is to update [Table 6-1](#) (Assessment Schedule) to include the visits at which the Enthesitis Evaluation must be done.

Amendment 1

Rationale for Amendment

The purpose for Amendment 1 is to update the following Sections and Tables.

- **Section 4.1:** Inclusion criteria number four (4) was updated to justify the need for a baseline skin scoring accordingly. Therefore, it was reworded to: a target psoriatic skin lesion and a PASI score of 1 or greater.
 - **Section 5.2:** Patients will receive treatment up to Week 48 and no treatment will be administered at the EOT Visit/Week 52.
 - **Section 5.5.8 and Table 5.1:** The table was rearranged to clarify that no biologics are allowed in the study. This is to prevent any further confusion that was observed since the study launched.
 - **Section 6:** Previous version required a 4 week waiting time even for those patients who are treatment naïve, and do not need a washout or repeat assessments. The related section of FUTURE 5 global protocol is adapted to prevent a 4 week waiting period for those patients. Screening will now be more flexible in duration up to 8 weeks prior to randomization based on the time required to wash out prior anti-rheumatic medications. Patients that do not require a washout can proceed onto the baseline visit once all inclusion criteria and none of the exclusion criteria are met.
 - **Section 6.4.2:** Was updated to remove the Independent Joint Assessor requirement. This is the first study evaluating various typical findings for PsA such as TJC, SJC, PASI, IGA, enthesitis, dactylitis [REDACTED]. Therefore, it is unlikely for the site personnel to have independent assessors for each evaluation. In order to best reflect the current standard of practice, it is per the Investigator's discretion to decide who will be performing the evaluations.
-

- **Section 6.4.6:** Updated to emphasize the importance that the Erythrocyte Sedimentation Rate test must be performed locally.
- **Section 6.5.6:** Updated to include that a serum β -hCG test will be performed in all women of child bearing potential at Screening Visit 2; and a local urine pregnancy tests will be performed at the specified visits as indicated in [Table 6-1](#).
- **Appendix 12.10:** The PROs Guidelines for the SitePad have been updated.

Protocol summary

Protocol number	CAIN457FUS01

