1.2 Purpose

The purpose of this study is to provide 16 week safety, efficacy and tolerability data in biologic naïve PsA patients with concomitant psoriatic skin lesions and evaluate the effect of secukinumab on PsA specific clinical findings such as dactylitis, enthesitis and psoriatic lesions. The study will also evaluate the early efficacy of the treatment at the first scheduled clinical visit after starting a treatment (i.e., at week 4) and investigate the remission status of all patients at each time points by evaluating the MDA, PASDAS and DAS28-CRP. This will be done in the blinded long term extension by increasing the dose to 300 mg in nonresponding

patients in 150 mg groups to confirm or support the role of higher IL-17A activity in PsA by evaluating the clinical response at every 12 weeks.

2 Study objectives

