150 mg dose in each of these studies, regardless of whether the loading dosing was i.v. (CAIN457F2306: 50.0% for 150 mg vs 17.3% for placebo) or s.c. (CAIN457F2312: 51.0% for 150 mg vs 15.3% for placebo), 150 mg is a sufficient dose to provide clinically and statistically significant efficacy, whereas higher loading doses of secukinumab do not appear to confer a greater response on the primary efficacy variable of ACR20 at Week 24. In Study CAIN457F2312, PASI75 and PASI90 response was assessed in the subgroup of patients who had $\geq 3\%$ skin involvement with psoriasis at baseline. For both PASI75 and PASI90 response rates, the difference to placebo at Week 24 was statistically significant for the secukinumab 150 mg and 300 mg doses (PASI75: 48.3%, $p = 0.0006$ and 63.4%, $p < 0.0001$; PASI90: 32.8%, $p = 0.0029$ and 48.8%, $p = 0.0002$, respectively). The percentage of responders increased as secukinumab dose increased, with the secukinumab 300 mg dose demonstrating a meaningful improvement over the secukinumab 150 mg dose (treatment differences between secukinumab 300 mg and 150 mg for PASI75 and PASI90 were 15.1% and 16.0%, respectively). Of note, the 75 mg s.c. loading (once weekly) followed by maintenance (once monthly) tested in CAIN457F2312 achieved a statistically significant but clinically lower effect size in ACR20 response of 29.3% and did not achieve statistically significant improvements in any of the efficacy variables tested in a pre-defined testing hierarchy, including PASI75, PASI90 DAS28 CRP, SF36 PCS, HAQ-DI©, ACR50, dactylitis and enthesitis.

This study is evaluating secukinumab 300 mg and 150 mg s.c. doses for the treatment of adults with active PsA and a baseline psoriatic skin lesions of PASI 1 and higher. As the phase 3 program suggested that patients with concomitant skin lesions may have more pronounced clinical benefits with 300 mg, all the placebo patients will receive secukinumab 300 mg after the completion of placebo controlled period (Week 16). The non-responders in Group 2 (150 mg patients) will receive secukinumab 300 mg after the completion of Week 16 as well as at every clinical visit until the completion of the study (Weeks 20, 24, 28, 32, 36, 40, 44 and 48) based on their responder status.

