Male and female patients aged at minimum 18 at time of consent, with active PsA fulfilling the CASPAR criteria (described in Appendix 2). Patients must have symptoms for at least 6 months with moderate to severe PsA and must have ≥ 3 tender joints out of 78 and ≥ 3 swollen joints out of 76 at baseline (dactylitis of a digit counts as one joint each).

Patients must have a target psoriatic skin lesion with a PASI score of 1 or greater at the time of screening.

A total of approximately 250 patients will be randomized in approximately 65 rheumatology/dermatology centers in the United States. A screening failure rate of approximately 30% and post-randomization loss to follow-up rate of 10% is anticipated. Patients who drop out after they have been randomized will not be replaced.

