4.1 Inclusion criteria

Patients eligible for inclusion in this study have to fulfill **all** of the following criteria:

1. Patient must be able to understand and communicate with the investigator and comply with the requirements of the study and must give a written, signed and dated informed consent before any study assessment is performed
2. Male or non-pregnant, non-lactating female patients at least 18 years of age
3. Diagnosis of PsA classified by CASPAR criteria and with symptoms for at least 6 months with moderate to severe PsA who must have had at Baseline ≥ 3 tender joints out of 78 and ≥ 3 swollen joints out of 76 (dactylitis of a digit counts as one joint each)
4. A target psoriatic skin lesion and a PASI score of 1 or greater
5. RF and/or Anti-cyclic citrullinated peptide (anti-CCP) antibodies negative at screening.
6. Patients who are regularly taking NSAIDs as part of their PsA therapy are required to be on a stable dose for at least 2 weeks before study randomization and should remain on a stable dose up to Week 16
7. Patients taking corticosteroids should be on a stable dose of ≤ 10 mg/day prednisone or equivalent for at least 2 weeks before randomization and must remain on a stable dose up to Week 16
8. Patients taking MTX (≤ 25 mg/week) are allowed to continue their medication if the dose is stable for at least 4 weeks before randomization and must remain on a stable dose up to study completion
9. Patients on MTX must be on folic acid supplementation at randomization
10. Patients who are on a DMARD other than MTX must discontinue the DMARD 4 weeks prior to randomization visit except for leflunomide, which should be discontinued for 8 weeks prior to randomization unless a cholestyramine washout has been performed.

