6.4.10 Minimal disease activity

The proportion of patients achieving minimal disease activity (MDA (Coates 2010) (5 of the 7 following: ≤ 1 tender joint count, ≤ 1 swollen joint count, PASI ≤ 1 or IGA ≤ 1 , patient pain VAS ≤ 15 , patient global VAS ≤ 20 , HAQ-DI ≤ 0.5 , tender enthesal points ≤ 1).

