6.4.14 Psoriasis Area and Severity Index (PASI)

The PASI assessment will be conducted for patients in whom at least 3% of the body surface area (BSA) was affected by psoriatic skin involvement at BL. The PASI assesses the extent of psoriasis on four body surface areas (head, trunk and upper and lower limbs) and the degree of plaque erythema, scaling and thickness. A PASI score ([Fredriksson and Pettersson 1978](#), [Weisman 2003](#), [Gottlieb 2005](#)) will be derived as indicated in [Table 6-2](#).

The head, trunk, upper limbs and lower limbs are assessed separately for erythema, thickening (plaque elevation, induration), and scaling (desquamation). The average degree of severity of each sign in each of the four body regions is assigned a score of 0-4. The area covered by lesions on each body region is estimated as a percentage of the total area of that particular body region. Further practical details help the assessment:

The neck is assessed as part of the head.

The axillae and groin are assessed as part of the trunk.

The buttocks are assessed as part of the lower limbs.

When scoring the severity of erythema, scales should not be removed.

Table 6-2 The PASI scoring system

Body region	Erythema (E)	Thickening (plaque elevation, induration)(I)	Scaling (desquamation) (D)	Area score (based on true area %)(A)*
Head (H)**	0=none 1=slight 2=moderate 3=severe 4=very severe	0=none 1=slight 2=moderate 3=severe 4=very severe	0=none 1=slight 2=moderate 3=severe 4=very severe	0 = 0% 1 = 1-9% 2 = 10-29% 3 = 30-49% 4 = 50-69% 5 = 70-89% 6 = 90-100%
Trunk, (T)***	0=none 1=slight 2=moderate 3=severe 4=very severe	0=none 1=slight 2=moderate 3=severe 4=very severe	0=none 1=slight 2=moderate 3=severe 4=very severe	0 = 0% 1 = 1-9% 2 = 10-29% 3 = 30-49% 4 = 50-69% 5 = 70-89% 6 = 90-100%
Upper limbs (U)	0=none 1=slight 2=moderate 3=severe 4=very severe	0=none 1=slight 2=moderate 3=severe 4=very severe	0=none 1=slight 2=moderate 3=severe 4=very severe	0 = 0% 1 = 1-9% 2 = 10-29% 3 = 30-49% 4 = 50-69% 5 = 70-89% 6 = 90-100%
Lower limbs (L)****	0=none 1=slight 2=moderate 3=severe 4=very severe	0=none 1=slight 2=moderate 3=severe 4=very severe	0=none 1=slight 2=moderate 3=severe 4=very severe	0 = 0% 1 = 1-9% 2 = 10-29% 3 = 30-49% 4 = 50-69% 5 = 70-89% 6 = 90-100%

* Percentage (not score) of body region (not whole body) affected will be entered in the eCRF

**Neck is assessed as part of the Head (H) body region.

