6.4.15 Investigator's Global Assessment (IGA mod 2011)

IGA mod 2011 will be conducted for overall psoriatic disease as indicated in [Table 6-3](#) for patients in whom at least 3% of the body surface area (BSA) was affected by psoriatic skin involvement at BL. It is recommended that the same evaluator conducts the assessment throughout the study wherever possible.

The IGA mod 2011 rating scale has been developed based on a previous version of the scale used in secukinumab phase II psoriasis studies in collaboration with health authorities in particular the FDA. The explanations/descriptions of the points on the scale have been improved to ensure appropriate differentiation between the points (see [Table 6-3](#)).

The IGA mod 2011 used in this study is static, i.e. it refers exclusively to the subject's disease state at the time of the assessments, and does not attempt a comparison with any of the subject's previous disease states, whether at baseline or at a previous visit.

[figure not shown]
The IGA mod 2011 score will be recorded in the eCRF at the given visits/time points of [Table 6-1](#).

[figure not shown]
Table 6-3 The IGA mod 2011 rating scale

Score	Short Description	Detailed Description
0	Clear	No signs of psoriasis. Post-inflammatory hyperpigmentation may be present.
1	Almost clear	Normal to pink coloration of lesions; no thickening; no to minimal focal scaling.
2	Mild	Pink to light red coloration; just detectable to mild thickening; predominantly fine scaling.
3	Moderate	Dull bright red, clearly distinguishable erythema; clearly distinguishable to moderate thickening; moderate scaling.
4	Severe	Bright to deep dark red coloration; severe thickening with hard edges; severe / coarse scaling covering almost all or all lesions.

Note: Involvement of nails is not part of the assessment.

Based on this scale, a subject will be considered as IGA 0 or 1 responder if the subject achieves a score of 0 or 1 and improved by at least 2 points on the IGA scale compared to baseline.

[figure not shown]

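### Protocol 6.4.14 and 6.4.15 limit PASI and IGA scoring to patients with at least 3% BSA, in conflict with entry on PASI of 1 or more; followed literally, some FAS patients would have no MDA/VLDA skin item

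*Protocol*

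**What the plan says.** Protocol 6.4.14 introduces the skin score with a limit: "The PASI assessment will be conducted for patients in whom at least 3% of the body surface area (BSA) was affected" at baseline. Protocol 6.4.15 places the same limit on IGA mod 2011, which is done "for patients in whom at least 3% of the body surface area (BSA) was affected by psoriatic skin involvement at BL".

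Other parts of the plan require or presuppose skin scores without a BSA limit:

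- Protocol section 4 (Population): "Patients must have a target psoriatic skin lesion with a PASI score of 1 or greater at the time of screening". Inclusion criterion 4 in section 4.1: "A target psoriatic skin lesion and a PASI score of 1 or greater". Neither sets a BSA minimum.
- Protocol 3.3 describes the population as "adults with active PsA and a baseline psoriatic skin lesions of PASI 1 and higher".
- Protocol 1.2 sets out to "investigate the remission status of all patients at each time points by evaluating the MDA, PASDAS and DAS28-CRP".
- SAP Table 5.5-1, item OTH02, treats a missing PASI total at an attended visit as a deviation, with no BSA condition.

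For MDA, Protocol 6.4.10 asks for "5 of the 7 following", and one of the seven items is PASI ≤ 1 or IGA ≤ 1. SAP 2.7.2 adds VLDA, which needs all seven. Protocol 9.5.1 and SAP 2.7.1 put secondary efficacy on the FAS. SAP 2.2 uses 3% BSA to define a Psoriasis Subset, and SAP 2.7.2 assigns PASI75/90/100 to it, but not MDA or VLDA. SAP 2.7.3 applies non-responder imputation to binary variables other than ACR and says nothing about single MDA items.

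**The concern.** MDA is a named secondary objective. Its skin item can be satisfied by either PASI or IGA, but both carry the same 3% BSA limit, so neither can stand in for the other. A patient who enters on PASI of 1 or more with less than 3% BSA would, on the literal text, be in the FAS with no skin item at all. VLDA would then be out of reach, and MDA would have to be decided either on six items or by calling the whole endpoint a non-response. In both cases the reported rate would no longer follow the stated definition of five out of seven for those patients, and it would be too low.

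**Working it through.** **Step 1. Check the PASI formula.** Protocol 6.4.14 gives region weights of 0.1 (head), 0.2 (upper limbs), 0.3 (trunk) and 0.4 (lower limbs), three signs scored 0 to 4, and an area score of 0 to 6. The maximum is 12 × 6 × (0.1 + 0.2 + 0.3 + 0.4) = 72, which is the figure stated there.

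**Step 2. Does PASI of 1 or more imply 3% BSA?** In Table 6-2 the area score is 1 from 1% to 9% of a region. The protocol takes the regions as about 10%, 20%, 30% and 40% of body surface. Slight signs throughout give a sign sum of 3.

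| Extent of disease | BSA | PASI |
|---|---|---|
| 1% of lower limbs | 0.4 × 1% = 0.4% | 0.4 × 3 × 1 = 1.2 |
| 5% of lower limbs | 0.4 × 5% = 2.0% | 0.4 × 3 × 1 = 1.2 |
| 1% of all four regions | 1.0 × 1% = 1.0% | 1.0 × 3 × 1 = 3.0 |

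All three meet the PASI part of criterion 4 and fall outside 6.4.14 and 6.4.15. The two groups are different.

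**Step 3. What follows below 3% BSA if nobody there is scored?**

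- VLDA needs 7 of 7, so it cannot be met.
- MDA has two readings under SAP 2.7.3: (a) the unscored item counts as not met, so 5 of the other 6 are needed; (b) the whole endpoint is imputed as non-response.

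**Step 4. Illustrative size.** The documents give neither the share below 3% BSA nor item rates. Assume seven independent items, each met with probability 0.5, and the same true rate in both BSA groups.

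- Full definition: P(≥ 5 of 7) = (21 + 7 + 1)/128 = 22.7%.
- Reading (a): P(≥ 5 of 6) = (6 + 1)/64 = 10.9%.
- Reading (b): 0%.

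With a share f below 3% BSA, the overall rate is (1 − f) × 22.7% + f × 10.9% under (a) and (1 − f) × 22.7% under (b).

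| Assumed share f | Patients of 250 | MDA, reading (a) | MDA, reading (b) |
|---|---|---|---|
| 0% | 0 | 22.7% | 22.7% |
| 10% | 25 | 21.5% | 20.4% |
| 30% | 75 | 19.1% | 15.9% |
| 50% | 125 | 16.8% | 11.3% |

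The result depends on the item rate. At 0.3 per item, MDA below 3% BSA goes from 2.9% to 1.1% under (a); at 0.7 it goes from 64.7% to 42.0%. Under the same assumption of equal true rates, overall VLDA falls by the full share f.

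**The case against.** The strongest reply is that this is a wording slip and no data were lost. Much supports it. Criterion 4 cannot be checked unless every candidate has a PASI. The Amendment 1 rationale says "Inclusion criteria number four (4) was updated to justify the need for a baseline skin scoring accordingly", which is context only but points the same way. OTH02 expects a PASI at attended visits regardless of BSA. A separate Psoriasis Subset would be largely redundant if only patients at or above 3% BSA were scored. Protocol 3.3 also shows 3% used as an analysis subgroup in an earlier phase 3 trial. Together these make an analysis filter the likelier intention. They do not settle it: entry scoring at screening says nothing about later visits, and 6.4.14 and 6.4.15 speak of conducting the assessment, not of analysing it.

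A second reply is that relevant text could not be read. The PASI and IGA rows of Table 6-1 are missing from the extracted text, as is SAP 2.13, which the SAP change log lists among the sections touched by the VLDA update. Either could say who was scored or how an unscored item is handled. That limits what can be said about consequences, but the wording of the two protocol sections would still conflict with the entry criterion.

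A third reply is that the figures rest on invented inputs. That is correct. Independence, equal item rates and the share below 3% BSA are all assumptions, and the numbers show only how the mechanism works.

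**Conclusion.** The conflict is real and in current text: 6.4.14 and 6.4.15 cannot both stand with entry on PASI of 1 or more, MDA evaluation in all patients, FAS analysis and OTH02. The 3% limit was probably intended only as an analysis filter. If it was followed as written, FAS patients below 3% BSA cannot reach VLDA and have MDA understated. The size is unknown; the illustrated fall from 22.7% to 19.1% or 15.9% assumes 30% of patients below 3% BSA and independent items each met in half of patients. If everyone was scored, the effect is zero.

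A reader might infer more than this, and the documents do not support it:

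- That skin data are in fact missing, or that reported MDA rates are biased. Nothing in the text shows that sites withheld scoring.
- That the whole FAS lacks the item. Only patients below 3% BSA at baseline could.
- That MDA is unattainable without it. Under reading (a), 5 of the other 6 items still suffice.
- That the main result is at risk. ACR20 uses no skin score, so the primary analysis and sample size are untouched. VLDA is not a protocol objective and entered the SAP after the Week 16 lock.

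**What to change.** 1. In Protocol 6.4.14 and 6.4.15, state that PASI and IGA mod 2011 are scored in all randomized patients at the scheduled skin visits. Keep 3% BSA only to define the Psoriasis Subset for PASI75/90/100, as SAP 2.2 and 2.7.2 already do.
2. Report by arm the number of FAS patients with baseline BSA below 3% who have neither PASI nor IGA at Week 16. If it is zero, nothing further is needed.
3. Only if it is not zero, report MDA and VLDA in the Psoriasis Subset as a supportive analysis. For patients below 3% BSA whose skin item was unscored by design, show MDA and VLDA with that item counted once as not met and once as met. These are bounds, not estimates: in the illustration above, MDA in that group is 10.9% with the item not met and (15 + 6 + 1)/64 = 34.4% with it met, around the full-definition 22.7%. Leave SAP 2.7.3 unchanged for ordinary missed scores at or above 3% BSA.

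For Week 16 data already locked, only items 2 and 3 can act. The cost is wording in two protocol sections, one count, a few minutes of skin scoring per visit in patients with little skin disease, and at most one or two extra tables. The subset analysis follows the full definition but has a smaller n.

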6.4.15 Investigator's Global Assessment (IGA mod 2011)

IGA mod 2011 will be conducted for overall psoriatic disease as indicated in [Table 6-3](#) for patients in whom at least 3% of the body surface area (BSA) was affected by psoriatic skin involvement at BL. It is recommended that the same evaluator conducts the assessment throughout the study wherever possible.

The IGA mod 2011 rating scale has been developed based on a previous version of the scale used in secukinumab phase II psoriasis studies in collaboration with health authorities in particular the FDA. The explanations/descriptions of the points on the scale have been improved to ensure appropriate differentiation between the points (see [Table 6-3](#)).

The IGA mod 2011 used in this study is static, i.e. it refers exclusively to the subject's disease state at the time of the assessments, and does not attempt a comparison with any of the subject's previous disease states, whether at baseline or at a previous visit.

[figure not shown]
The IGA mod 2011 score will be recorded in the eCRF at the given visits/time points of [Table 6-1](#).

[figure not shown]
Table 6-3 The IGA mod 2011 rating scale

Score	Short Description	Detailed Description
0	Clear	No signs of psoriasis. Post-inflammatory hyperpigmentation may be present.
1	Almost clear	Normal to pink coloration of lesions; no thickening; no to minimal focal scaling.
2	Mild	Pink to light red coloration; just detectable to mild thickening; predominantly fine scaling.
3	Moderate	Dull bright red, clearly distinguishable erythema; clearly distinguishable to moderate thickening; moderate scaling.
4	Severe	Bright to deep dark red coloration; severe thickening with hard edges; severe / coarse scaling covering almost all or all lesions.

Note: Involvement of nails is not part of the assessment.

Based on this scale, a subject will be considered as IGA 0 or 1 responder if the subject achieves a score of 0 or 1 and improved by at least 2 points on the IGA scale compared to baseline.

[figure not shown]

6.4.17 Physician's global assessment of fingernail disease severity (VAS)

The physician's assessment of nail disease activity will be performed using 100 mm VAS ranging from no disease activity to maximal disease activity, after the question "*After you have viewed all the fingernails of a subject, consider all aspects of the subject's fingernails and place a vertical line on the scale giving a global assessment of their fingernails*".

6.4.19 Appropriateness of efficacy assessments

The efficacy assessments used in this study are the standard assessments used across many psoriatic arthritis trials.

